Usual Care: at time of positive pregnancy test done in the woman's village the Health Aide provides brief advice to quit (< 3 minutes) to women who use tobacco. Health aide gives all women (tobacco users and non-users) written materials on risks of tobacco use.	x	x
Health Aide or village clinic staff will provide the woman with a study flyer and asks her if she would like to learn more about the study. If yes, the health aide or clinic staff will provide contact information to the research coordinator.	x	x
Research coordinator screens the woman for eligibility.	x	x
Research coordinator consents and enrolls eligible/interested pregnant women and conducts a baseline assessment.		
Follow-up assessments conducted with enrolled women by the research coordinator at 12 weeks post-enrollment, at week 36 gestation, and weeks 8 and 26 postpartum.	x	x
Intervention Villages Only: Native Sister delivers a community-wide social marketing campaign in her home village over a 2-year period. Native Sister delivers 6 telephone based peer counseling sessions to enrolled women during pregnancy (weeks 1, 2, 4 post-enrollment) and postpartum (weeks 2, 4, 6)		x

Rationale for a Group Randomized Design:

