Our prior work indicated that female Elders (as defined above) would be most credible to deliver the intervention. Although it would be practical to have village-based health aides deliver the intervention, credibility is an issue because most health aides use tobacco. Research highlights respect for and credibility of Elders in the transmission of cultural knowledge and health information in AI/AN communities. Elders also encourage and reinforce community ownership of problems and problem solving, i.e., the cultural value of collective responsibility. Recruiting Elders from their home village will enhance the dissemination and sustainability of the intervention. Further, a local Elder is likely to be more credible and effective at changing social norms around tobacco use than one from another village. When we experienced difficulties finding a sufficient number of Native Sisters or during staff turnover we hired an individual residing in Bethel who delivered the intervention to other villages. In addition, someone hired in one Intervention village may have served as the "Native Sister" for another Intervention village. The study team has experience with hiring and working with village-based Elders/community members. Moreover, the YKHC study coordinator was trained as a back-up interventionist. During times of Native Sister staff turnover, and staff turnover with respect to the YKHC study coordinator, Mayo research staff was asked by prior YKHC managers overseeing the project to fill in (calls for 20 participants total were assigned to Mayo staff). Currently, however, there are two Native Sisters hired and assigned to make the intervention calls for all intervention villages.

Consistent with prior community-based studies, the social marketing campaign will last about two years (27 months). Native Sisters will attempt to contact all enrolled women for six telephone-based peer counseling sessions (3 during pregnancy, 3 postpartum). A face-to-face peer counseling session will be offered if it is

feasible at the village health clinic. We chose 6 sessions total based on evidence of a dose response relationship between number of sessions and successful tobacco use outcomes. While there is no evidence that pharmacotherapy is effective during pregnancy, use of NRT and other medications will be encouraged by the Native Sister during the postpartum period by referral to the YKDRH clinical cessation program.

Randomization:

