We selected villages for participation in this study based on our prior work and established relationships, and villages that had sufficient numbers of pregnant women each year. In 2011, over a 9 month period there were 16 villages with at least 15 women seen for a 1st prenatal visit (Table 1). This estimate was conservative because it does not reflect all women with a positive pregnancy test. Sixteen villages were stratified based on village size (<600 and >600) and randomly assigned to receive the intervention (8 villages) or control condition (8 villages).

Table 1. Village count of pregnant women seen for a 1st visit Jan-Sept 2011 (excludes Bethel)

# pregnant women	# villages
1-9	20
10-14	9
15-19	7
20-25	8
26-30	1
31-35	0
36-44	3

The research coordinator and study staff met with the respective village tribal councils and village health aide staff of all 16 villages to enlist their participation. We have successfully used this approach in our previous group-randomized trial in this region.

Recruitment of pregnant women within each village will occur over an 25-month period. We attempted to enroll at least 22 pregnant women from each of the 16 villages, accounting for an estimated rate of attrition of 10% based on prior studies due to miscarriage, abortion or fetal demise, to achieve a final sample of at least 320 women eligible for follow-up. Recruitment delays were encountered and thus NIH funding was extended from 5 to 6 years (see Table 4). We will request a no cost extension from NIH for a 7th project year which will enable us to complete analyses and dissemination as remaining funds permit.

Recruitment:

A study logo that consists of a baby in womb and the text “*Healthy Pregnancies*” was created by Northwest Strategies. The logo was placed on all recruitment materials, and will be used on any communications from the research coordinator or study team members.

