Treatment Self-regulation Questionnaire (TSRQ) (intrinsic vs. extrinsic motivation for change) (156,157)		15	X	✗	X	X	X
Yupik Wellness Questionnaire (i.e., positive cultural activities) (101)		24	X	✗	X	X	X
Perceived Stress Scale (158) and CES-D Depression Scale (159)		4/20	X	✗	X	X	X
Prenatal care utilization (161)		2	X	✗	X		

To reduce participant burden, the week 12 pregnancy assessment was reduced to only one form (program evaluation). No questions were added. We noted early in the follow-up phase that the week 12 assessment was not feasible to complete at the intended time frame. This is because most women enrolled at ≥ 24 weeks gestation, in which case the week 36 assessment coincides with the 12 week post-enrollment assessment. Of 352 participants enrolled, 222 (63%) were ≥ 24 weeks gestation at enrollment. Moreover, only 9% of women (33/352) enrolled before 12 weeks gestation. The consent form acknowledges that the week 12 assessment would be conducted depending on when they enroll in the study. To accommodate varying enrollment/assessment schedules and to standardize the assessment process for research staff and participants, we will ask the week 12 program evaluation questions at the week 36 assessment, and participants will receive a gift card for completing each of these assessments. Thus, the potential number of gift cards provided and assessments conducted with participants will remain the same.

Intervention (Intervention Villages only):

Native Sister Intervention Components

Native Sister hiring and training:

Native Sisters were hired by YKHC as a sub-contracted employee. The Native Sister's role is one of a study ambassador for the Healthy Pregnancies Study in their village. Native Sisters must meet the following qualifications:

- Be considered an Elder: 55 years and older or someone who is younger but who is seen as credible in the community/or as a leader
- Speak both English and Yup'ik
- Tobacco-free (no tobacco use in the last 6 months)
- Believe that no tobacco use is safe when a woman is pregnant

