Additionally, the Native Sister will distribute all campaign media to community members (e.g., handing out the digital story DVDs and promotional items, and displaying posters). A power point presentation was developed for the Native Sisters. During the training the Native Sisters will individualize their presentation. The Native Sister will seek advice from the village councils on implementing the campaign and develop community contacts and volunteers who can assist. However, it has not been feasible for the Native Sisters to conduct presentations or outreach activities on a consistent basis, which reflects the current practice. YKHC

staff plans to conduct village travel whereby promotional and other campaign material will be distributed in the intervention villages.

A process evaluation checklist titled “Native Sisters Events Total” was created for the Native Sisters to document delivery of specific community and individual level intervention components based on existing measures. Using this checklist, each Native Sister will record distribution of media such as number of DVDs and brochures provided; and presentations/outreach activities and number of people in attendance. Individual-level components recorded will include number of sessions completed (of 6 total), format (telephone/in-person) and duration. These checklists will be provided to the YKHC research coordinator.

Campaign Materials:

All campaign materials and promotional items were created by Northwest Strategies, Inc., except for the digital stories DVD which was created by nDigiDreams, Inc. Both design companies are Native owned. A study logo “*Healthy Pregnancies*” was created by Northwest Strategies and was placed on all campaign materials. The materials to be distributed in the intervention villages are:

- 1) Posters
- 2) Flyers
- 3) Digital stories DVD
- 4) Promotional items: baby bibs, hoodies, and note pads
- 5) Brochure targeted to pregnant women

In addition, all village members in each of the 8 intervention villages were mailed an oversized postcard to ensure that all community members are exposed to the campaign. The postcards were mailed in a box from Mayo Clinic to each village post office for distribution. The postcards therefore did not have any names or identifying information.

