up or who do not provide biochemical confirmation classified as using tobacco. The analysis will be supplemented with multiple imputation methods to classify lost to follow-up as tobacco users or non-users. GEE will also be used to examine condition differences on the point prevalence tobacco use rates at 12 weeks/week 36 gestation, and at 8 weeks postpartum. Because only 14 df are available for the test of the intervention we will employ a small sample correction to the standard GEE. For these analyses, the stratification factor (village size) will be adjusted for in the analysis. Based on the biochemically confirmed tobacco use status at baseline, in an exploratory fashion we will examine potential treatment effects separately among baseline non-tobacco users and tobacco users respectively using GEE. Within intervention villages only, exposure dose will be tested as a predictor of tobacco use at 36 weeks gestation and 6 months postpartum using GEE. A similar analysis will be performed using the intervention implementation index to examine potential dose response effects. Assuming an ICC of 0.01 and an effective sample size of 135 subjects in the intervention arm after correction for the ICC, there will be 80% power to detect an effect size of at least 0.5 standard deviation units when examining the association of intervention exposure (i.e., continuous measure) and abstinence rates. Potential village differences on intervention exposure or implementation will be summarized graphically and compared using GEE. The percentage of enrolled participants who complete 6- month follow-up postpartum (retention) will be compared between intervention and control villages using GEE.

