We will follow procedures suggested by MacKinnon to assess mediation (**Aim 2**), fitting three GEE models to the data. We will first estimate the intervention effect separately for the dependent variable (with regression adjustment for covariates). That model provides an estimate of the total effect of the intervention, which MacKinnon labels C. Next we will estimate the intervention effect for each mediator (with regression adjustment for covariates); that model provides an estimate of the effect of the intervention on the mediator, which MacKinnon labels A. Finally we will estimate the mediated intervention effect for the dependent variable by adjusting for the mediator (and covariates); that model provides an estimate of the unmediated (i.e., direct) intervention effect, which MacKinnon labels C, and the intervention-adjusted effect of the mediator on the dependent variable, which MacKinnon labels B. Assuming an ICC of 0.01 and an effective sample size of 270 subjects after correction for the ICC, there will be 80% power to detect an effect size of at least 0.35 standard deviation units for paths A and B assuming a two-sided, alpha=0.05 test at 6-months postpartum.

Treatment condition differences on changes in other variables targeted (see Table 4) will be examined using GEE with a logit (binomial outcome) or identify (continuous outcome) links as appropriate.

We will summarize the cost of the program per pregnant woman enrolled (reached) along with cost per woman abstinent from tobacco at 6 months postpartum follow-up using descriptive statistics.

Endpoints

Primary:

Biochemically confirmed tobacco abstinence at 6-months post-partum.

Secondary:

Biochemically confirmed tobacco abstinence at end of pregnancy. Also, changes in proposed theory-based mediators of intervention efficacy.

Project Timeline

We have received approval from NIH to extend out the study timeline from 5 to 6 years total. We are currently beginning the 5th year of our 6-year NIH grant. Table 4 shows the timeline for the remaining Phase II

activities. We will request from NIH a 7th project year as a no-cost extension to complete analyses and dissemination if necessary and long as remaining funds permit.

Table 4

PROJECT TIMELINE, YEARS 3-7,
Dates: May 1, 2015 – April 30, 2020

Activity	Year 3 2015-2016				Year 4 2016-2017				Year 5 2017-2018				Year 6 2018-2019				Year 7 2019-2020 No Cost Extension					

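### In intervention villages the enrolment baseline can follow exposure to the campaign, so analyses of change in mediators and targeted variables may miss part of its effect

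*Combined protocol and SAP*

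**What the plan says.** **Analyses that use baseline.** Under Endpoints, the secondary list gives late-pregnancy abstinence and then adds: "Also, changes in proposed theory-based mediators of intervention efficacy". For the remaining measures, the Phase II Data Analysis Plan states: "Treatment condition differences on changes in other variables targeted (see Table 4) will be examined using GEE". (Table 4 is the project timeline; the variables are in Table 2, Measures and Schedule of Assessments.) The same plan says, as an exploratory step, that "we will examine potential treatment effects separately among baseline non-tobacco users and tobacco users respectively using GEE".

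**Campaign.** Figure 1 describes it for intervention villages: "Native Sister delivers a community-wide social marketing campaign in her home village over a 2-year period". Intervention Reach, Delivery and Duration puts its length at about 27 months. It is not triggered by a woman's enrolment. Under Campaign Materials, residents of the eight intervention villages "were mailed an oversized postcard to ensure that all community members are exposed to the campaign"; no mailing date is given.

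**Baseline.** The Randomization section says: "Recruitment of pregnant women within each village will occur over an 25-month period". Under Procedures, the baseline interview, which covers self-efficacy and social norms, follows each woman's consent and enrolment. No survey before the campaign is described.

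**The concern.** A change score isolates an intervention effect when baseline precedes exposure in both arms. Here that holds in control villages, apart from the small contamination risk that the protocol accepts. In an intervention village, a woman who enrols after the campaign has begun may already have been influenced by it. Subtracting her baseline removes that part of the effect in one arm only.

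At stake is how the community component is read. The design rests on shifting village norms. A null difference in change could mean that norms did not move, or that they had moved before enrolment. As planned, the analysis would not separate the two. Programme evaluation, which measures campaign exposure, is not scheduled at baseline in Table 2. The plan compares baseline demographics between arms but does not mention baseline mediators. Nothing adjusts for, or tabulates by, time since the campaign began.

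**Working it through.** **1. Timing.** The campaign lasts about 27 months and recruitment 25 months. If they began together, all recruitment falls inside the campaign. Table 4 starts its recruitment and intervention-delivery rows in the same column. That row cannot date the campaign, however: it also covers counselling, and its 15 quarterly marks (15 × 3 = 45 months) do not match 27 months. So baseline *can* follow exposure, but how often it does, and by how long, is not documented.

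**2. The plan's own figure for mediators.** Inputs from the Power Statement and the Aim 2 paragraph: N = 320, 20 women per village, ICC 0.01, two-sided alpha 0.05, effect 0.35 SD.
- Design effect = 1 + (20 − 1) × 0.01 = 1.19.
- Effective N = 320 / 1.19 = 268.9 (stated: 270).
- Power with 135 per arm = Φ(0.35 × √(135/2) − 1.96) = Φ(0.916) = 82% (stated: 80%).

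The figure reproduces. It belongs to mediation paths A and B at 6 months postpartum; the plan gives no size for a change score. It serves below only as a yardstick.

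**3. What each analysis estimates.** Let D be the full effect at follow-up, f the share of D already present at baseline, and ρ the correlation between baseline and follow-up. With equal SDs of 1:
- change score: D(1 − f), with SD √(2(1 − ρ));
- follow-up adjusted for baseline: D(1 − ρf), with SD √(1 − ρ²);
- follow-up level only: D, with SD 1, provided the arms are otherwise comparable.

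**4. Illustration.** D = 0.35, 135 per arm, ρ = 0.5 (so the change SD is 1). The documents give neither f nor ρ; both are assumed.

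| f | Change estimate (SD) | Power |
|---|---|---|
| 0 | 0.35 | 82% |
| 10% | 0.315 | 74% |
| 25% | 0.26 | 58% |
| 50% | 0.18 | 30% |
| 75% | 0.09 | 11% |

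The follow-up comparison stays at 0.35 SD and 82% in every row. The baseline-adjusted estimate falls less, to 0.306 SD at f = 25% and 0.26 SD at f = 50%, with power of 83% and 70%. Power depends on ρ: at f = 25%, change-score power is about 45% for ρ = 0.3 and about 80% for ρ = 0.7. The loss in the estimate does not depend on ρ.

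**5. Reach.** The primary comparison is tobacco use at 6 months postpartum, adjusted for village size. It subtracts no baseline. The mediation models are described as intervention effects on each mediator with covariate adjustment, and no baseline mediator is named as a covariate. The problem therefore bears directly on the secondary endpoint for mediators and on the other targeted variables.

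**The case against.** The strongest reply is that little of the effect could precede baseline. Under Individual components, enrolled women received the DVD and brochures after the baseline questionnaires. Under Community components, outreach was not feasible on a consistent basis, and village travel to distribute material was still planned although recruitment was complete. Only five Native Sisters were found, and some covered other villages. Women who contacted a Native Sister before enrolling did so to ask about the study, which is not the same as receiving intervention. The six counselling sessions all follow baseline. This stands as a limit on size: f may be small, and it is zero if the campaign had no effect before enrolment. It does not remove the asymmetry between arms.

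The second reply is that dropping baseline has its own cost. Women were recruited after villages had been assigned, with different postcards by arm, and village numbers ranged from 2 to 42. Baseline gives some protection against selection and imbalance. This also stands, and it is why levels belong beside change and should not replace it.

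Three stronger readings are tempting, and the documents do not support them.
- **Aim 2 is undermined as a whole.** The mediation models are not written as change analyses.
- **Late enrolment shows heavy prior exposure.** The protocol reports: "Of 352 participants enrolled, 222 (63%) were ≥ 24 weeks gestation at enrollment". But the loss depends on calendar time since the campaign began in the village and on actual contact with it, not on gestation at enrolment.
- **The split by baseline tobacco status is biased against the intervention, because campaign-induced quitters relapse more than other non-users.** The pilot figures in the Power Statement do not show this. Of 400 prior users, 332 used prenatally and 68 quit; 276 (69%) used at 6 weeks postpartum, including about 43 of the quitters (63%). Continuing users therefore number 276 − 43 = 233, or 233/332 = 70%. Of the 432 others, 324 used prenatally and about 302 (70%) used postpartum. If 70% of the 324 continued (assumption), that is about 227, leaving 302 − 227 = 75 of the 108 prenatal non-users. Use among all 176 prenatal non-users is then (43 + 75)/176 = 67%, against 63% in quitters. No bias in the claimed direction is established.

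**Conclusion.** The structural point holds. In intervention villages baseline can follow exposure, so the planned change analyses estimate the effect after enrolment only. As measures of the whole intervention they lean toward no effect, provided that the campaign worked in the intended direction and that any early shift lasted to follow-up. The amount cannot be derived from the documents and may be small. The 0.26, 0.18 and 0.09 SD figures illustrate assumed shares and are not estimates.

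The primary endpoint is untouched. The mediation models are touched only if the baseline mediator enters as a covariate, and then by the smaller factor 1 − ρf. The exploratory split by baseline tobacco status conditions on a measure that may follow exposure; that calls for a caveat, not a claim about direction. This is a cheap improvement to reporting and interpretation.

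**What to change.** In the Phase II Data Analysis Plan:
1. Report the between-arm difference in the follow-up level of each mediator and targeted variable alongside the change analysis, using GEE adjusted for village size.
2. Tabulate baseline norms, self-efficacy and tobacco status by arm, and by calendar time of enrolment or by months since campaign start where known.
3. State that change results, and the split by baseline tobacco status, are conditional on a measure that may follow exposure, so a null change is not evidence that the campaign had no effect.
4. Say whether the baseline mediator is a covariate in the mediation models, and point the cross-reference to Table 2.

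**Cost.** Wording and one table, with no new data from participants. Campaign start dates by village are not in the documents and would have to come from study records; calendar time of enrolment is the fallback.

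**Downside.** A difference in levels, or at baseline, may also reflect recruitment selection or chance imbalance across 16 villages. The table cannot separate these from a campaign effect, so levels and change should be read together.

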After providing written informed consent, the woman was enrolled. Next, the research staff administered a baseline interview by phone or in-person to assess socio-demographic information; nicotine dependence and readiness to quit (for tobacco users); theory-based measures (mediators), e.g., self-efficacy, social norms and cultural beliefs about tobacco use; and other variables targeted by the intervention such as second hand smoke exposure (See Table 2 below). These measures have established psychometric properties. Efforts will be made to obtain follow-up assessments from all participants by the research staff who does not provide the intervention. In-person assessments will occur when the woman is scheduled for an appointment in Bethel (at week 36 gestation (if enrolled before this time point) and at 8 weeks postpartum). The week 36 assessment will be attempted in-person at the Bethel pre-maternal home or by phone before or after delivery. All other follow-up assessments and for women whose in-person assessment is missed (e.g., due to pregnancy complications, triage to Anchorage for delivery, or lack of time at the visit), will be conducted by phone. The assessments are similar to those completed at baseline. Participants will receive a \$25 gift card for completing each assessment at baseline and follow-up for up to a total of \$125. Each assessment is estimated to last about 60 minutes.

Self-reported tobacco use will be assessed using a multiple choice response format recommended for pregnant smokers. A saliva specimen will be collected for analysis of cotinine from all participants and

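### Arm differences on changes in the targeted variables and mediators are planned with change undefined and no baseline covariate named; modelling the follow-up value adjusted for baseline is at least as precise for continuous outcomes and resolves the logit problem for binary ones.

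*Combined protocol and SAP*

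**What the plan says.** Three places in the Combined protocol and SAP bear on this.

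- **Data Analysis Plan, Phase II (other targeted variables).** "Treatment condition differences on changes in other variables targeted (see Table 4) will be examined using GEE with a logit (binomial outcome"; an identity link is given for continuous outcomes. The table cited there, Table 4, is the project timeline. The measures are in Table 2 (Measures and Schedule of Assessments).
- **Endpoints, Secondary.** After tobacco abstinence at the end of pregnancy, the list continues: "Also, changes in proposed theory-based mediators of intervention efficacy". Neither the reference time point nor the estimator is given.
- **Data Analysis Plan, Aim 2 (mediation).** The path A model is described as follows: "Next we will estimate the intervention effect for each mediator (with regression adjustment for covariates". The covariates are not listed, and the model is not described as a change-score analysis.

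The one adjustment factor named is in the paragraph on the tobacco-use models: "For these analyses, the stratification factor (village size) will be adjusted for in the analysis". No section names the baseline value of the outcome as a covariate for the mediators or the other targeted variables.

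The baseline data exist. Under Procedures, the baseline interview covers "theory-based measures (mediators), e.g., self-efficacy, social norms and cultural beliefs about tobacco use; and other variables targeted by the intervention", and of the follow-ups it says: "The assessments are similar to those completed at baseline". Table 2 marks baseline and at least one later visit for each of these measures.

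**The concern.** A plain difference score fixes the slope on baseline at 1. When the correlation between baseline and follow-up is below 1, that slope is too steep. The extra baseline noise is carried into the arm comparison. Below r = 0.5 a difference score is noisier than ignoring baseline altogether, because 2(1−r) then exceeds 1. Fitting the slope instead uses the same data and, with equal variances and a reasonable sample, is never less precise.

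For yes/no items the problem is different in kind. Subtracting two 0/1 values gives −1, 0 or 1, which is not a binomial outcome. If change means subtraction, the logit model in the plan cannot be fitted without a choice that the plan does not state.

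At stake are the mediator secondary endpoint, the reading of path A, and the comparisons of the other targeted variables. These estimates could be less precise than the collected data allow, and the analyst would be left to choose between methods that give different answers.

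**Working it through.** **Inputs from the documents.** 16 villages, 8 per arm; 320 women in all, average 20 per village (Power Statement). For mediation: "Assuming an ICC of 0.01 and an effective sample size of 270 subjects after correction for the ICC", and "there will be 80% power to detect an effect size of at least 0.35 standard deviation units for paths A and B", two-sided alpha 0.05. **Assumed, not in the documents:** r; equal variances at baseline and follow-up; and that the plan's SD unit is that of the raw score.

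**Step 1: reproduce the plan's figure.**
- Design effect = 1 + 19 × 0.01 = 1.19. Effective N = 320/1.19 = 268.9, against 270 stated, so about 135 per arm.
- SE of an arm difference in SD units = √(2/135) = 0.1217.
- Detectable effect at 80% power = (1.960 + 0.842) × 0.1217 = 0.341 SD, consistent with the stated 0.35.
- Power at 0.35 SD = Φ(0.35/0.1217 − 1.960) = 82%, against 80% stated.

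The plan's figure reproduces with a unit-variance outcome. That corresponds to the follow-up value alone, or to a change score at exactly r = 0.5.

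**Step 2: compare the two analyses, continuous outcome.** In units of the raw-score variance:
- change score: 2(1−r)
- follow-up adjusted for baseline: 1−r²
- ratio, adjusted to change: (1−r²)/[2(1−r)] = (1+r)/2
- variance saved: (1−r)/2; interval width saved: 1 − √[(1+r)/2]

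The detectable effect is 0.341 times the square root of the variance in each case.

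| Assumed r | Variance, change | Variance, adjusted | Variance saved | Interval narrower by | Detectable SD, change / adjusted | Power at 0.35 SD, change / adjusted |
|---|---|---|---|---|---|---|
| 0.3 | 1.40 | 0.91 | 35% | 19% | 0.403 / 0.325 | 68% / 85% |
| 0.5 | 1.00 | 0.75 | 25% | 13% | 0.341 / 0.295 | 82% / 91% |
| 0.7 | 0.60 | 0.51 | 15% | 8% | 0.264 / 0.244 | 96% / 98% |
| 0.8 | 0.40 | 0.36 | 10% | 5% | 0.216 / 0.205 | above 99% for both |
| 0.9 | 0.20 | 0.19 | 5% | 2.5% | 0.152 / 0.149 | above 99% for both |

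**Step 3: clustering.** A simulation of 16 villages, with equal and unequal sizes, gave savings of 15% to 36% for r from 0.7 to 0.3 when the village-level correlation equals the woman-level one. With an assumed village-level correlation of 0.9 and ICC 0.01 to 0.03, the saving fell to about 7% to 30%.

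**Step 4: when there is no loss.** In the same simulation, a change score with baseline also in the model gave exactly the same treatment estimate as the follow-up value with baseline in the model. The loss arises only if baseline is left out.

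**Step 5: difference in value.** If the arms differ at baseline by D, the change score subtracts D in full and the adjusted analysis subtracts rD (equal variances). The two estimates differ by (1−r)D. With D equal to one standard error (0.12 SD) and r = 0.5, that is 0.06 SD.

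**Step 6: binary outcomes.** The formula in Step 2 does not carry over to a logit model, so no percentage is claimed there.

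**The case against.** The strongest reply is that the plan never says it will subtract. The baseline is not named as the reference point in either sentence about change. Specifying a logit link for binomial outcomes suggests that something else may be meant. A condition-by-time GEE would fit that wording, and the −1/0/1 problem would then disappear. Path A already adjusts for covariates, and baseline could be among them; by Step 4 nothing would then be lost. All of this stands. It turns the point into a conditional one without removing it: change is undefined, and an unconstrained condition-by-time model would not recover the precision.

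The second reply concerns the baseline itself. Women were recruited over 25 months after villages had been assigned, while a campaign of about 27 months ran (Randomization; Intervention Reach, Delivery and Duration). Table 4 starts recruitment and intervention delivery in the same quarter. Postcards differed by arm, and some women came to the study through the Native Sister (Recruitment; Campaign Materials). A later enrollee's baseline norms may therefore already reflect exposure. A reader might infer that baseline adjustment is sound whenever the baseline was taken; the documents do not support that. This does not favour a change score, though, which subtracts any such difference in full.

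A reader might also infer that large chance imbalance is likely with only 8 villages per arm. At the plan's ICC of 0.01 the SE of a baseline difference is 0.12 SD, so a difference beyond 0.25 SD would arise by chance only about 4% of the time.

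**Conclusion.** The point holds in conditional form. The plan compares arms on change without defining it or naming a baseline covariate. If it means an unadjusted difference score, continuous outcomes carry 2/(1+r) times the woman-level variance of the adjusted analysis, and binary outcomes do not fit the stated link.

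The size depends on r, which the documents do not give. At r = 0.3 a change score would fall short of the plan's own power target for path A (68% against 80% at 0.35 SD) and the adjusted analysis would meet it. At r of 0.7 or more both exceed the target and the practical gain is small.

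Two stronger readings are tempting. One is that the mediators are definitely analysed as raw changes from baseline. That rests on an endpoint label, while the only mediator model described has unlisted covariate adjustment, so baseline adjustment is neither stated nor excluded. The other is that a fixed 15% to 35% of precision is lost. That range is variance rather than interval width, applies only to continuous outcomes, and needs r between 0.3 and 0.7.

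The primary tobacco endpoint and the late-pregnancy tobacco endpoint are not analysed as changes and are unaffected.

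**What to change.** In the Data Analysis Plan and Endpoints sections:

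1. For each mediator and each other targeted variable, fit the GEE to the follow-up value (identity or logit link as appropriate) with arm, village-size stratum and the woman's own baseline value as covariates. Report the adjusted arm effect in place of a difference in change.
2. List the path A covariates and include the baseline value of the mediator among them.
3. Point the cross-reference to Table 2, Measures and Schedule of Assessments, and give its title, because the document has another Table 2 (Focus Group Domains).
4. Report the baseline arm difference for each of these variables, and show the follow-up comparison without baseline adjustment as a sensitivity check, since baseline may partly reflect campaign exposure.

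The cost is wording and one extra set of model runs; no new data are needed. There are two small downsides. With a logit link the arm effect becomes conditional on baseline and is no longer a marginal odds ratio, which should be said when it is reported. If the arms differ at baseline because of early exposure, the adjusted estimate removes part of that effect, which is why item 4 is needed.
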